A total of 380 subjects were randomized and received at least one dose of study drug, of which 68.7% had HCV genotype 1a, 31.3% had HCV genotype 1b, 42.1% were treatment-naïve, 36.1% were prior pegIFN/RBV null responders, 8.2% were prior pegIFN/RBV partial responders, and 13.7% were prior pegIFN/RBV relapsers.

The SVR₁₂ rates for subjects with compensated cirrhosis treated with 3-DAA + RBV for 12 or 24 weeks were 91.8% and 95.9%, respectively. Virologic failure was noted in 13/208 (6.3%) subjects (on treatment virologic failure: n = 1; relapse: n = 12) receiving the 12-week regimen and 4/172 (2.3%) subjects (on treatment virologic failure: n = 3; relapse: n = 1) receiving the 24-week regimen.

Analyses of subgroups suggest that the overall difference in SVR₁₂ rates was driven largely by a lower SVR₁₂ rate among genotype 1a prior null responders who received 12 weeks of treatment, while other subgroups had comparable response rates when treated for 12 or 24 weeks. Thus, a 12-week treatment regimen is recommended for all patients with cirrhosis with the exception of genotype 1a prior null responders, for whom 24 weeks of treatment provides a higher SVR.

Integrated Safety Results

A summary of treatment-emergent adverse events from the pooled analyses of data from the phase 3 studies is presented in [Table 2](#). A majority of subjects experienced at least one event, but most subjects experienced events that were mild in severity. Rates of severe adverse events and adverse events leading to discontinuation were low across studies but numerically higher in the study of subjects with cirrhosis.

Table 2. Overview of Treatment-Emergent Adverse Events (AE)

	Placebo-Controlled		Regimen-Controlled		Cirrhotics	
	12-wk 3-DAA + RBV	12-wk PBO	12-wk 3-DAA + RBV	12-wk 3-DAA	12-wk 3-DAA + RBV	24-wk 3-DAA + RBV
Events, %	N = 770	N = 255	N = 401	N = 509	N = 208	N = 172
Subjects \geq 1 AE	89.0	76.9	82.8	75.0	91.8	90.7
Severe AE	3.5	0.4	1.0	1.2	6.7	7.6
Grade 3 or 4 AE	3.9	0.8	3.0	2.0	7.7	8.1
Serious AE	2.1	0.4	2.2	1.4	6.3	4.7
AE leading to discontinuation	0.8	0.4	0.5	0.4	1.9	2.3
Deaths	0.1 ^a	0	0	0	0	0

PBO = Placebo

a. Lung cancer.

The most common adverse events regardless of causality are listed in Table 3.

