3.1 Differences Statement

The combination of 3-DAA with or without RBV for 12 and 24 weeks was explored in treatment-naïve and pegIFN/RBV treatment-experienced HCV GT1-infected subjects, with (12 and 24 weeks) or without (12 weeks only) compensated cirrhosis, in several phase 3 studies. These Phase 3 studies have been conducted in a randomized, controlled, double-blind or open-label fashion. This study is a Phase 3b, single arm, open-label study in approximately 600 treatment-naïve and IFN/RBV treatment-experienced subjects with or without compensated cirrhosis.

This is the first study to evaluate SVR₁₂ and clinical outcomes through 5 years following treatment with 3-DAA with or without RBV for 12 or 24 weeks in chronic HCV GT1-infected subjects. The study population comprises HCV GT1a- and 1b-infected subjects in the United States who are treatment-naïve or IFN/RBV treatment-experienced. The study will include up to 25% of subjects with compensated

cirrhosis which approximates the projected prevalence among chronic HCV-infected subjects in the United States.¹⁵

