4.3 Sample Size

Assuming 4% of subjects do not achieve SVR₁₂ and assuming the 5-year event rate of the composite clinical outcome is 20% in the non-SVR₁₂ subjects, with a 75% reduction in SVR₁₂ subjects (Hazard Ratio of 0.25),^{1,2} then based on two-sample log rank test (using EAST 6.0), a sample size of at least 2000 subjects enrolled in TOPAZ-I (planned to enroll 1650 subjects) and TOPAZ II (planned to enroll 600 subjects) provides greater than 80% power to reject the null hypothesis of no difference between SVR₁₂ and non-SVR₁₂

subjects in the rate of clinical outcome events. Power calculations were based on a dropout rate of up to 20% for the hazard ratio.

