10.0 Efficacy Analysis

10.1 General Considerations

The primary efficacy analysis on clinical outcomes will be performed on all subjects in the ITT population as defined in Section 5.1. All other efficacy analyses will be performed on the ITT-II population.

Treatment effects will be evaluated based on a two-sided significance level of 0.05 (when rounded to three decimal places). The data from the ITT-II population will be presented in one column/row as it represents the labelled treatment.

Plasma HCV RNA levels will be determined for each sample collected by the central laboratory using the COBAS[®] AmpliPrep/COBAS[®] TaqMan[®] HCV Test, v2.0. The lower limit of quantification (LLOQ) and the lower limit of detection (LLOD) is 15 IU/mL. HCV RNA results that are detectable but not quantifiable are reported as "< 15 IU/mL" and results that are not detectable are reported as "-NON-DETECTED."

Assessment of Clinical Outcomes

Incidence of the following clinical outcome events will be collected during the 12/24 weeks of treatment and the 5-year (PT Week 260) Post-Treatment Period. The data reported on the "Clinical Outcome" eCRFs will be adjudicated by an independent outcome committee and results of the adjudication will be added to the "Clinical Outcome" eCRFs:

- All-cause death: Death due to any cause.
- Liver-related death: Death as the result of a liver-related cause.
- Liver decompensation: Development of any of the following conditions: ascites, hepatic encephalopathy, or variceal bleeding.

- Liver transplantation: any subject who had a liver transplantation
- Hepatocellular carcinoma (HCC): development of HCC in any subject at any time during the study. HCC is defined by histologic confirmation or a > 1 cm mass lesion on cross-sectional imaging that meets the diagnostic criteria for HCC according to EASL guidelines.
- Composite of any of the above outcomes.

Definitions for HCV RNA Efficacy Endpoints

Note that a confirmed quantifiable post-treatment value is defined as two consecutive post-treatment HCV RNA measurements \geq LLOQ. During treatment, a confirmed quantifiable value is defined as any two consecutive HCV RNA values \geq LLOQ, either both during treatment or at the final treatment measurement and the next consecutive post-treatment measurement.

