10.3 Primary Efficacy Analysis

The primary efficacy analysis will be conducted among subjects in the ITT population as described in Section 5.1. HCV RNA values and SVR₁₂ will be imputed as described in Section 6.3.

The primary efficacy endpoint is to assess the effect of response to treatment (as assessed by SVR₁₂ status) on clinical outcomes by comparing the time to incidence of the following events between subjects who achieve SVR₁₂ and those who do not.

- All-cause death
- Liver-related death
- Liver decompensation
- Liver transplantation
- Hepatocellular carcinoma

- Composite of any of the above outcomes

For each of the six event types as listed above, a subject's time to event will be defined as the number of days from the first day of study drug dosing for the subject to the day the subject experiences an event of interest. All events of interest will be included, regardless of whether the event occurred while the subject is still taking study drug or has previously discontinued study drug. If the subject does not experience an event of interest nor has the subject died (all-cause death), the subject's data will be censored at the date of the subject's last available assessment of clinical outcomes. For subjects with no post-baseline assessment, the subject's data will be censored on the first day of study drug dosing. All-cause death is a censoring event for liver-related death, liver decompensation, liver transplantation and hepatocellular carcinoma. Time to the composite of clinical outcomes is the time to the first occurrence of any clinical outcome.

For each of the six event types, the distribution of time to event will be estimated for subjects who have achieved SVR₁₂ and those who haven't using Kaplan-Meier methodology and compared between the subjects who have achieved SVR₁₂ and those who haven't using the log-rank test.

For each of the six event types, the 1-, 2-, 3-, 4-, and 5-year event-free survival rate will be estimated using Kaplan-Meier methodology and a 95% confidence interval will be constructed separately for those who have achieved SVR₁₂ and those who have not. For each of the six event types, a Cox proportional hazards (PH) model will be constructed to include all the baseline characteristics as described in Section 7.1, SVR₁₂ status, and other variables as appropriate.

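### The log-rank test and Kaplan-Meier curves in SAP 10.3 are not stratified by cirrhosis or study, so these crude comparisons can partly reflect baseline cirrhosis, and the SAP does not say whether they or the adjusted Cox model are the primary inference.

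*SAP*

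**What the plan says.** SAP 10.3 takes the combined ITT-I and ITT-II population. For each of six event types it estimates Kaplan-Meier curves by SVR12 status and compares subjects with SVR12 and "those who haven't using the log-rank test". It names no stratification factor. The one- to five-year event-free rates are likewise split only by SVR12. SAP 10.1 sets a "two-sided significance level of 0.05".

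SAP 4.3 derives its power of more than 80% from a two-sample log-rank test on at least 2,000 subjects, again with no strata mentioned.

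SAP 10.3 then adds, for each event type, a Cox model with SVR12 status, every baseline characteristic in Section 7.1 and further variables as appropriate. Section 7.1 includes fibrosis stage (F0-1, F2, F3, F4) and Child-Pugh score with a non-cirrhotic level. Protocol 8.1.2.1 and the synopsis name Cox regression for the primary endpoint but list no covariates.

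No section ranks the log-rank test against the Cox model. Study (TOPAZ-I or TOPAZ-II) is not named as a stratum or covariate; country appears in Section 7.1, but among the demographics.

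**The concern.** SVR12 status is an outcome of treatment, not an assignment. If cirrhosis raises both the chance of failing treatment and the chance of a liver event, the non-SVR12 group holds more cirrhotics and has more events even when response itself changes nothing.

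The protocol supports both links. In Section 3.0, the SVR12 rates of cirrhotics "treated with 3-DAA + RBV for 12 or 24 weeks were 91.8% and 95.9%, respectively", against 96.2% and 96.3% in non-cirrhotics on the RBV-containing regimen for 12 weeks. The same section describes decompensation and hepatocellular carcinoma as complications of cirrhosis. Cirrhotics are not a small share: in Section 3.1, "The study will include up to 25% of subjects with compensated" cirrhosis.

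What is at stake is how the log-rank p-values and the Kaplan-Meier contrasts are read for all six endpoints. If the log-rank test is taken as the primary result because the power was computed for it, part of what is reported as the benefit of response could be baseline disease severity.

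**Working it through.** **1. The plan's own figure.** Inputs from SAP 4.3: "Assuming 4% of subjects do not achieve" SVR12; the five-year "event rate of the composite clinical outcome is 20% in the" non-SVR12 group; "Hazard Ratio of 0.25"; N = 2,000; dropout up to 20%. I take exponential event and dropout times over five years.

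- Yearly hazards: non-SVR12 −ln(0.80)/5 = 0.0446; SVR12 0.25 × 0.0446 = 0.0112; dropout −ln(0.80)/5 = 0.0446.
- Expected events = n × λ/(λ+δ) × [1 − exp(−5(λ+δ))]. Non-SVR12: 80 × 0.5 × 0.36 = 14.4. SVR12: 1,920 × 0.2 × 0.2434 = 93.5. Total 107.9.
- Schoenfeld power = Φ(|ln 0.25| × √(107.9 × 0.04 × 0.96) − 1.96) = Φ(0.86), about 0.806.

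The stated power reproduces. Direct simulation of the log-rank test at these inputs gives about 0.97, so the claim of more than 80% is met.

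**2. Failure by cirrhosis.**

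- Cirrhotic, 12 weeks: 100 − 91.8 = 8.2%. Cirrhotic, 24 weeks: 100 − 95.9 = 4.1%.
- Non-cirrhotic with RBV: 3.7-3.8%. GT1b non-cirrhotic without RBV: 0-1% (Protocol 3.2).
- Cirrhotics under the current Protocol Table 5, weighting Protocol Table 1 by the Study M13-099 mix (42.1% naïve, 36.1% null, 8.2% partial, 13.7% relapser; 68.7% GT1a). GT1a at 24 weeks: 7.1 × (0.421 + 0.361) = 5.55%. GT1b at 12 weeks: 14.3 × 0.082 = 1.17%. Together: 0.687 × 5.55 + 0.313 × 1.17 = 4.2%.

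The last figure assumes that subtype and prior response are independent and that every GT1a cirrhotic receives 24 weeks.

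**3. Events by cirrhosis.** Carcinoma at about 3% per year (Protocol 3.0) gives 1 − 0.97⁵ = 14% over five years for that component alone. I assume a five-year composite risk of 15-25% in cirrhotics. The documents give no composite rate for non-cirrhotics; I assume 2-3%.

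**4. What pooling does when SVR12 has no effect.** Worked case: 25% cirrhotic, failure 8.2% versus 3.5%, five-year risk 20% versus 2% (hazards 0.0446 and 0.0040).

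- Cirrhotic share of non-SVR12: 0.25 × 0.082 / (0.25 × 0.082 + 0.75 × 0.035) = 43.9%.
- Cirrhotic share of SVR12: 0.25 × 0.918 / (0.25 × 0.918 + 0.75 × 0.965) = 24.1%.
- Crude hazard ratio (ratio of mean hazards): (0.241 × 0.0446 + 0.759 × 0.0040) / (0.439 × 0.0446 + 0.561 × 0.0040) = 0.63.

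The same formula, with simulated null trials (N = 2,000, 20% dropout, 25% cirrhotic, risks 15-25% versus 2-3%), gives:

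| Failure, cirrhotic vs other | Crude HR | Unstratified test rejects | Stratified by cirrhosis |
|---|---|---|---|
| 8.2% vs 3.5% | 0.62-0.70 | about 20-36% | 4-6% |
| 6.0% vs 3.5% | 0.73-0.80 | about 10-17% | 4-6% |
| 4.2% vs 3.2% | 0.85-0.90 | about 6-9% | 4-6% |
| 4.2% vs 3.7% | 0.93-0.95 | about 5-7% | 4-6% |

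If GT1b subjects pull non-cirrhotic failure down to 2.5%, the rate at 4.2% cirrhotic failure rises to as much as about 15%.

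**5. Load on the Cox model.** Each Section 7.1 baseline characteristic is entered once, demographics not counted: subtype 2, IL28B 2, prior treatment 7, HCV RNA 1, HOMA-IR 1, fibrosis stage 3, Child-Pugh 3, tobacco 2, alcohol 2, and ten single terms (FibroTest, albumin, creatinine clearance, MDRD GFR, platelets, diabetes, depression or bipolar disorder, bleeding disorder, APRI, FIB-4). That is 33, or 34 with SVR12. 107.9 / 34 = about 3 composite events per parameter, with about 14 events in the non-SVR12 group. No component outcome can have more events than the composite. F4 and the Child-Pugh levels encode nearly the same split, and FibroTest, APRI and FIB-4 overlap.

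**6. Cost of stratifying.** With a hazard ratio of 0.25 within strata and about 20% events in the non-SVR12 group, the cirrhosis-stratified test keeps about 97% simulated power (unstratified 97-99.6%).

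**The case against.** The strongest reply is that the plan already adjusts for cirrhosis. The Cox model stands in the same section, includes fibrosis stage and Child-Pugh score, and is the method the protocol names for the primary endpoint. A log-rank power calculation does not make the log-rank test the primary inference. This stands, and it confines the bias to the log-rank p-values and the Kaplan-Meier contrasts.

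The second reply is that the 8.2% failure rate comes from 12 weeks of treatment, while GT1a cirrhotics now default to 24 weeks. This also stands: at about 4.2% versus 3.7% the inflation nearly disappears. It is not conclusive, because investigators may select 12 weeks, some earlier enrollees stay on 12 weeks, GT1b cirrhotics receive 12 weeks, and these documents do not give TOPAZ-I's regimens by subgroup.

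Third, Protocol 5.6.1 calls the analyses descriptive, with no hypothesis tests planned. That sits poorly with a significance level in SAP 10.1 and a power statement in SAP 4.3, and it does not help a reader of the crude curves.

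What the Cox model leaves open is which result is primary, whether study enters at all, and whether cirrhosis would be retained if so large a model had to be cut down.

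**Conclusion.** The point holds as an avoidable weakness in the crude comparisons and an unsettled choice of primary inference. Its size rests on assumed rates: the cirrhosis share in TOPAZ-I (1,650 of the 2,250 planned subjects) and the non-cirrhotic event rate are not in the documents, and 25% is TOPAZ-II's upper limit (150 of about 600) applied to both studies. Over the settings tabulated, the unstratified test rejects a true null in about 5% to 36% of trials.

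A reader might infer three stronger things that the documents do not support:

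- That the primary objective goes unanswered. The adjusted Cox model addresses it.
- That a positive result would merely be cirrhosis. The lowest crude hazard ratio from confounding alone was 0.53 over all settings examined, including failure of 8.2% versus 2.6%; it never approached the planned 0.25.
- That regional differences bias the result. No study effect is given or can be quantified here; the case for stratifying by study is only that two separately run studies are pooled.

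**What to change.** In SAP 10.3:

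- Stratify the log-rank test by study (TOPAZ-I, TOPAZ-II) and baseline cirrhosis (F4 versus F0-F3).
- Present the Kaplan-Meier estimates by cirrhosis as well as by SVR12.
- Use the same strata in the Cox model, and preferably replace the full Section 7.1 list with a short prespecified set of covariates.
- State that the stratified or adjusted comparison is the primary inference and that the crude one is descriptive.

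The cost is a few sentences in the SAP and almost no power. Study is known for every subject, and TOPAZ-II records fibrosis stage at enrolment. The sponsor should confirm that TOPAZ-I records it in the same categories.

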5.6 Discussion and Justification of Study Design

5.6.1 Discussion of Study Design and Choice of Control Groups

The combination regimen of ABT-450/r/ABT-267 and ABT-333 with or without RBV for 12 and 24 weeks has been evaluated in treatment-naïve and pegIFN/RBV treatment-experienced HCV GT1-infected subjects, with or without compensated cirrhosis, in the Phase 3 studies. Based upon the results from Studies M11-646, M13-098, M13-961, M13-389, M14-002 and M13-099 (discussed in detail in Section 3.0), AbbVie plans to evaluate the same combination regimen used in the Phase 3 studies in a study population of treatment-naïve and IFN/RBV treatment-experienced HCV GT1-infected subjects, with or without compensated cirrhosis. The intention of this study is to assess the effect of treatment response on long-term clinical outcomes and evaluate the SVR₁₂ following treatment with ABT-450/r/ABT-267 and ABT-333, with or without RBV. Given the above considerations, it is anticipated that the study design will maximize the SVR rates in the population. As such, the absence of randomization, blinding and control groups is appropriate. No hypothesis testing is planned; statistical analyses will be descriptive.

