3.0 Introduction

This statistical analysis plan (SAP) describes the statistical analyses to be completed by AbbVie Statistics and Statistical Programming for Study Protocol M14-222.

Study M14-222 (TOPAZ-II) and companion Study M14-423 (TOPAZ-I) are designed together and shares the primary objective of evaluating the effect of treatment response (assessed by the status of SVR₁₂, i.e., HCV ribonucleic acid (RNA) < lower limit of quantification [LLOQ] 12 weeks following treatment) on long-term clinical outcomes in adults with genotype 1 (GT1) chronic hepatitis C virus (HCV) infection who received treatment with ABT-450/r/ABT-267 and ABT-333 with or without ribavirin, as measured by all-cause death, liver-related death, liver decompensation, liver transplantation, and hepatocellular carcinoma.

In the TOPAZ-I and TOPAZ-II studies, the primary objective is to be assessed, based on the data from both studies combined. The studies differ based on geographic region (this study will be conducted in the US while the TOPAZ-I study will be conducted outside the US) and based on certain procedures that are not related to the primary outcome. For example, this study will utilize a Subject Care Plan Model to facilitate subjects' adherence to the study drug and the TOPAZ-II study will assess the long-term change from baseline in liver elastography.

This SAP provides details to guide the analyses for baseline, efficacy, and safety variables and describes the populations and variables that will be analyzed and the statistical methods that will be utilized. An interim analysis (after all subjects reach Post-Treatment [PT] Week 12 or prematurely discontinue the study) and an end of study analysis will be conducted for Study M14-222. Analyses will be performed using SAS[®] Version 9.3 (SAS Institute, Inc., Cary, NC) or later under the UNIX operating system.

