7.1 Demographic and Baseline Characteristics

Demographics include age, weight, height and BMI as continuous variables, and sex, race, ethnicity, age category (< 55 years or ≥ 55 years] and [< 65 or ≥ 65 years]), birth year (< 1945 , 1945 to 1965, > 1965), country, and BMI category (< 30 kg/m² or ≥ 30 kg/m²).

Baseline characteristics will include: HCV genotype 1 subtype (1a, 1b, 1-other), IL28B genotype ([CC, CT, or TT] and [CC or non-CC]), prior treatment history (treatment-naïve [IFN-eligible, IFN-ineligible] or IFN-based treatment-experienced [null responder, partial responder, relapser, relapse/breakthrough, nonresponder, IFN or pegIFN intolerant]), baseline HCV RNA levels ([continuous {use log₁₀ HCV RNA}] and [$< 800,000$ IU/mL or

$\geq 800,000$ IU/mL]), baseline HOMA-IR (< 3 or ≥ 3 mU \times mmol/L²), baseline fibrosis stage (F0-1, F2, F3, or F4), baseline Child-Pugh score (non-cirrhotic, 5, 6, or > 6), baseline FibroTest score, baseline albumin (continuous), baseline albumin (< 35 or ≥ 35 g/L), baseline creatinine clearance (GFR by Cockcroft Gault) (Continuous; < 30 mL/min, $\geq 30 - 49$ mL/min, $\geq 50 - 89$ mL/min, or ≥ 90 mL/min), baseline GFR by MDRD (continuous; < 30 , $30 - 59$, $60 - 89$, ≥ 90 mL/min/1.73m²; < 60 mL/min/1.73m² or ≥ 60 mL/min/1.73m²), baseline platelet count (continuous; $< 90 \times 10^9/L$ or $\geq 90 \times 10^9/L$; $< 50 \times 10^9/L$ or $\geq 50 \times 10^9/L$; $< 100 \times 10^9/L$ or $\geq 100 \times 10^9/L$; and $< 150 \times 10^9/L$ or $\geq 150 \times 10^9/L$), tobacco (user, ex-user, or non-user) and alcohol (drinker, ex-drinker, or non-drinker) use status, history of diabetes, history of depression or bipolar disorder, history of bleeding disorders, AST to platelet ratio index (APRI) (continuous; ≤ 2.0 or > 2.0), and Fibrosis-4 score (FIB-4) (continuous; ≤ 3.25 or > 3.25).

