In addition, stepwise logistic regression will be performed on both SVR₁₂ and virologic failure (on-treatment virologic failure or relapse) using subgroup variables described

above as predictors of response. Some variables will be treated as continuous to decrease the chance of separation or quasi-separation and some variables may be eliminated if missing for many subjects.

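### SAP 10.3 puts the whole Section 7.1 table list into every Cox model: little harm for the composite, but imprecise and unstable SVR12 hazard ratios for rare components

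*SAP*

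**What the plan says.** SAP 10.3 plans Kaplan-Meier estimates and a log-rank test by SVR12 status for each of five components and their composite. For each it then says that "a Cox proportional hazards (PH) model will be constructed to include all the baseline characteristics as described in Section 7.1", plus SVR12 status "and other variables as appropriate". It gives no form for each variable, no minimum number of events, no penalisation, and no rule for aliased terms or missing covariates.

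Section 7.1 is written for the baseline tables. It opens "Baseline characteristics will include: HCV genotype 1 subtype (1a, 1b, 1-other), IL28B genotype ([CC, CT, or TT] and [CC or non-CC]), prior treatment history" and continues through viral load, fibrosis, Child-Pugh, renal, platelet and lifestyle items, several in both continuous and categorical form. Age and sex stand in a separate sentence: "Demographics include age, weight, height and BMI as continuous variables, and sex, race, ethnicity".

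SAP 3.0 says "the primary objective is to be assessed, based on the data from both studies combined", and SAP 4.3 gives the planned sizes as "TOPAZ-I (planned to enroll 1650 subjects) and TOPAZ II (planned to enroll 600 subjects". Study is not a listed covariate; country, which would separate the two studies, appears only among the demographics.

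Two comparisons within the plan are useful. For the logistic regression of SVR12, SAP 10.5 says "Some variables will be treated as continuous to decrease the chance of separation or quasi-separation" and allows predictors with many missing values to be dropped; 10.3 has no such safeguard. SAP 6.3 provides for no imputation of baseline covariates.

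**The concern.** SVR12 groups are not randomised. Protocol 8.1.2.1 names the Cox model for comparing them, and it is the only planned comparison that adjusts for confounding. A long covariate list with few events inflates the variance of the SVR12 log hazard ratio and tends to push the estimate away from 1. Here that means overstating the benefit of SVR12. The same list is applied whatever the event count.

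Nor can the list be used literally. The Child-Pugh level for subjects without cirrhosis duplicates fibrosis F0–F3. The level above 6 should be almost empty, because Protocol 5.2.2 excludes a score of 7 or more. APRI and FIB-4 are built partly from platelets, which are also listed. Someone must choose forms and drop terms. The study is open-label and SVR12 is analysed at the interim, so those choices are better fixed in writing beforehand.

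**Working it through.** **1. Reproduce the plan's figure.** Inputs from SAP 4.3: N = 2,000, 4% without SVR12 (80 v 1,920), 20% five-year composite rate without SVR12, hazard ratio 0.25, dropout up to 20%. I take dropout as exponential over five years.
- Hazard without SVR12 = −ln(0.8)/5 = 0.0446 per year; with SVR12 it is a quarter of that, 0.0112; dropout hazard 0.0446.
- Events without SVR12: 80 × 0.5 × (1 − 0.8²) = 14.4.
- Events with SVR12: 1,920 × 0.2 × (1 − 0.8^1.25) = 93.5.
- Total 107.9. Schoenfeld power: Φ(√(107.9 × 0.04 × 0.96) × ln 4 − 1.96) ≈ 80.5%, which agrees with the stated figure of over 80%.
- At N = 1,650 + 600 = 2,250: 16.2 + 105.2 = 121.4 events. Other readings of dropout and of the 75% reduction give about 90 to 135.

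**2. Count coefficients**, one form each: subtype 2, IL28B 2, prior treatment 7, HCV RNA 1, HOMA-IR 1, fibrosis 3, Child-Pugh 3, FibroTest 1, albumin 1, Cockcroft-Gault 1, MDRD 1, platelets 1, tobacco 2, alcohol 2, diabetes 1, depression/bipolar 1, bleeding 1, APRI 1, FIB-4 1 = 33. With SVR12, 34.
- 107.9/34 = 3.2; 121.4/34 = 3.6.
- Without the aliased and the empty Child-Pugh terms, 32 remain: 3.4 to 3.8.

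**3. Is all-cause death sparse?** Protocol 3.0 quotes five-year mortality of 6.7% with SVR and 14.4% without.
- No dropout: 1,920 × 0.067 + 80 × 0.144 = 128.6 + 11.5 = 140.
- With dropout as in step 1: 115.4 + 10.4 = 126.

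These rates come from an interferon-era cohort and may not transfer. On them, however, deaths are not few, and the composite, which contains every death, has at least as many events.

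**4. Effect of the list (simulation).** N = 2,000, true hazard ratio 0.25, 20% dropout, 2,000 runs per row. Covariate distributions and effects are assumed, and no covariate is missing. The short model has 7 coefficients: SVR12, fibrosis stage, age, sex, platelets.

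| Events | Median HR, full v short | SD of log HR | Variance ratio | 95% CI coverage |
|---|---|---|---|---|
| 108 | 0.24 v 0.25 | 0.32 v 0.29 | 1.22 | 92.7% v 94.9% |
| 54 | 0.23 v 0.25 | 0.48 v 0.44 | 1.19 | 93.1% v 94.7% |
| 34 | 0.22 v 0.24 | 0.60 v 0.53 | 1.28 | 94.0% v 95.9% |
| 20 | 0.21 v 0.24 | 0.77 v 0.63 | (0.773/0.634)² = 1.49 | 94.3% v 96.5% |

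A second simulation used other assumed covariates and a short model with 5 coefficients besides SVR12.
- 108 events: hazard ratio 3–6% lower, variance 13–18% larger, coverage 94–95%.
- 25 events: log hazard ratio lower by 0.08 to 0.13, variance 23–40% larger.
- 15 events: lower by 0.18 to 0.33, variance 2.4 to 3.8 times as large.

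A third, shorter run gave 0.245 v 0.249 for the composite. At 20 events it gave 0.21 v 0.25 (SD 0.79 v 0.61). At 10 events it gave 0.13 v 0.20, coverage 86% v 96%, and 7% of full-list fits diverged.

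**5. Other models.**
- At 20 events, SVR12 plus cirrhosis with a Firth fit gave median 0.22, SD 0.64, coverage 96%, always finite. The full and 7-coefficient models were each finite in 96.6% of runs.
- SVR12 alone, where non-response clusters in cirrhosis, gave medians of 0.17 to 0.20. Removing all covariates is therefore not a remedy.

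**The case against.** The case for leaving 10.3 alone has force.
- The composite is the only powered endpoint and is barely affected. Protocol 5.6.1 says "No hypothesis testing is planned; statistical analyses will be descriptive". This stands.
- All-cause death is probably not sparse. This stands, subject to the cohort caveat.
- Down to 20 events the full-list interval still covers at about 94%, and the shift is small against a standard deviation of 0.77. This stands. The cost at that count is mainly precision; coverage fails only at about 10 events.
- The reduced Firth fit hardly moves the estimate back (0.22 v 0.21, truth 0.25). This also stands: its gain is in precision and stability.
- Full adjustment guards against confounding. Missing data and early discontinuation can count as non-SVR12, so behavioural factors could confound, and the first simulation's short model omitted only one weak confounder. For the composite this is a genuine trade-off and the sponsor's choice.

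None of this supports using the same list for a component with 10 or 20 events.

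A reader might infer that age and sex are excluded from the model. The documents do not support that: the Section 7.1 title covers demographics as well, and the open-ended clause in 10.3 would admit them.

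**Conclusion.** The point holds for the rarer components, such as liver transplantation, liver-related death, decompensation and HCC. At about 20 events the full list raises the variance of the SVR12 log hazard ratio by roughly 50% (about 68% in the third run) and moves the estimate away from 1. At about 10 events the model is unstable. This rests on assumed covariates, a true hazard ratio of 0.25, and low counts that the documents neither state nor exclude.

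Two stronger readings should be resisted.
- That 3.2 to 3.6 events per coefficient invalidates the primary comparison or its power. The power refers to the log-rank test, which has no covariates, and the composite hazard ratio stays usable: about 2–6% lower, variance 13–22% larger, coverage 93–95%.
- That the list alone explains hazard ratios that cannot be estimated. At 20 events full and short models failed equally often, because few events fall in the non-SVR12 group.

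This is a cheap improvement to the plan. Loss of subjects with missing covariates and stratification by study were not simulated.

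**What to change.** In SAP 10.3:
- State one form per variable and drop aliased terms, for example the Child-Pugh level for subjects without cirrhosis when fibrosis stage is in the model.
- Stratify by study (TOPAZ-I, TOPAZ-II).
- State how missing covariates are handled, and replace the open-ended clause with named variables.
- Set an event count in advance. For any event type below it, make a short pre-specified model primary: SVR12 plus cirrhosis or fibrosis stage and, where events allow, age and one liver marker. Use a penalised fit if needed. Report the full-list model there as a sensitivity analysis.
- For the composite and all-cause death the sponsor may keep the fuller adjustment, with a short model alongside. With the 7 coefficients simulated above, the composite has 107.9/7 = 15.4 to 121.4/7 = 17.3 events per coefficient.

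The covariates and the threshold are the sponsor's to choose. The cost is SAP wording, with no new data collection. The downside is less adjustment for weaker confounders in the sparse-component models, which the retained full-list analysis lets a reader judge.
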